#### 4.6. Schedule of assessments

Time-line	Activity/Treatment	Measurements
Day 1	Consent obtained; randomization; study drug administration by randomized group; vital signs monitoring.	SpO 2 (%), PaO 2 (mmHg), CRP (mg/L), PaO 2 /FiO 2 (mmHg)*, baseline data collection §
Day 3	Treatment continued, as defined above	CRP (mg/L), Worst daily PaO 2 /FiO 2 (mmHg)*, WHO clinical progression score
Day 7	Treatment continued, as defined above	CRP (mg/L), Worst daily PaO 2 /FiO 2 (mmHg)*, WHO clinical progression score

Day 14	Treatment continued, as defined above	CRP (mg/L), Worst daily PaO 2 /FiO 2 (mmHg)*, WHO clinical progression score
Day 28		Patient's outcome determined (mortality, total days of mechanical ventilation, days of invasive mechanical ventilation, days of noninvasive mechanical ventilation) and final data collection °
Hospital discharge		Patient's outcome determined (mortality, days of hospitalization)

\* The type of respiratory support (low-flow oxygen therapy, HFNC, NPPV, IMV, ECMO) under which the PaO2/FiO2 is obtained must be always specified in the appropriate section of the data collection form.

[figure not shown]
§ Baseline data should include:

- a) Date of birth
- b) Sex
- c) BMI
- d) Smoke (yes/no/former)
- e) Date of the onset of symptoms
- f) Date of hospitalization
- g) Date of randomization
- h) Type of respiratory support at randomization (i.e., low-flow oxygen, HFNC, NPPV)
- i) Comorbidities (COPD, Bronchiectasis, Asthma, Other respiratory disease, Pre-existing Diabetes, Atrial fibrillation, Coronaropathy, Chronic heart failure, Other relevant disease of the heart and large vessels, Pulmonary embolism/chronic thromboembolism, Other conditions requiring long-term anticoagulation, Systemic hypertension, Autoimmune Disease, OSA/OHS, Chronic Kidney Disease, Minor stroke, History of Cancer)

°Other data to be collected:

- a) Date of treatment initiation
- b) Date of full-dose treatment completion
- c) Date of de-escalation completion
- d) Deviation from protocol (yes/no; if yes, date of deviation and reason for deviation)
- e) Remdesivir (yes/no)
- f) Anticoagulation:
  - LMWH (prophylactic/anticoagulant)
  - Unfractionated heparin
  - Warfarin

- NOAC
- g) Relevant in-hospital therapies other than home therapy continuation, prophylactic antibiotics, (specify drug and dosage)
- h) NPPV (yes/no; if yes dates of start/end, in case of switch to IMV and then re-initiation of NPPV, enter only the end date of the second NPPV session)
- i) IMV (yes/no; if yes dates of start/end)
- j) HFNC (yes/no)
- k) ECMO (yes/no; if yes specify date of ECMO start and end)
- l) Tracheostomy (yes/no; if yes specify date of tracheostomy)
- m) Pronation (yes/no)
- n) Adverse events related to study treatment (Anaphylaxis, Agitation, Psychosis, Insomnia, Hyperglycemia/diabetes of new onset, Other: specify)
- o) In-hospital complications (Bradycardia, Diarrhea, Increased liver enzymes, Hypotension, Hypokalemia, Superinfection – specify microorganism, Shock requiring vasopressors not induced by the study drug, Acute renal failure, Disseminated Intravascular Coagulation, Acute myocardial infarction, Stroke, Atrial fibrillation or other major arrhythmias, Cardiorespiratory arrest, Pulmonary embolism, Other: specify).
- p) Date of hospital discharge
- q) Date of death

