## 2.2. Objectives

We hypothesize that in patients hospitalized for COVID-19 pneumonia requiring respiratory support (either oxygen supplementation, HFNC, NPPV), the methylprednisolone protocol is superior to the dexamethasone protocol in improving clinical outcomes.

The primary objective is to assess the efficacy of the methylprednisolone protocol in improving survival by day 28 compared to the dexamethasone protocol.

The secondary objectives are to compare efficacy of the two protocols in achieving:

- a) Reduction in the need and duration of mechanical ventilation
- b) Reduction in hospital mortality
- c) Reduction in the duration of hospitalization
- d) Reduction in duration of requirement for oxygen supplementation

Additional end-points include anti-inflammatory potency based on longitudinal reduction in systemic C-reactive protein levels and reduction in disease progression based on the WHO clinical progression scale.(9)

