##### Secondary outcome measures

- Number of days free from mechanical ventilation (either NPPV or IMV) by study day 28 in both arms
- Number of days of hospitalization among survivors in both arms
- Proportion of patients requiring tracheostomy in both arms
- C-reactive protein level (mg/L) at study day 3, 7 and 14 in both arms
- PaO2/FiO2 ratio (mmHg) at study day 3, 7 and 14 in both arms
- WHO clinical progression scale at study day 3, 7 and 14 in both arms(9)

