### 5.2. Data collection and management

A clinical database using REDCap® trial data management system will be developed with a web hosting facility. Electronic case report forms (eCRFs) will be developed to collect all clinical and laboratory related information. The trial database will include baseline information, information on demographics (age, gender), underlying illnesses, baseline and follow-up clinical and laboratory data for the purpose of assessment of clinical outcome. All data queries and corrections will be jointly conducted by the study team prior to database lock. The study team at the University of Trieste, Centro di Riferimento Oncologico of Aviano, and the Institute for Infectious Diseases “L. Spallanzani” of Rome will manage the data and will conduct quality control of the data. All analyses performed, the Clinical Study Report(s) and the final data set will be archived together according to the standard operating procedures and the guidelines of the University Hospital of Cattinara.

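### Item h of section 4.6 drops the dates around an interrupted NPPV course, so unventilated gaps count as ventilated; objective (d), oxygen duration, has no outcome and no dates

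*Protocol*

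**What the plan says.** **Ventilation.** The first secondary outcome in Protocol section 4.5 is "Number of days free from mechanical ventilation (either NPPV or IMV) by study day 28 in both arms". The day-28 row of the schedule in section 4.6 also lists "total days of mechanical ventilation, days of invasive mechanical ventilation, days of noninvasive mechanical ventilation" as results to be determined. It does not say whether these counts are entered directly or derived from dates.

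The dates are in the list of other data in the same section. Item h asks for the start and end of NPPV, with this rule for an interrupted course: "in case of switch to IMV and then re-initiation of NPPV, enter only the end date of the second NPPV session". Item i asks separately for "IMV (yes/no; if yes dates of start/end").

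**Oxygen.** Secondary objective (d) in section 2.2 is "Reduction in duration of requirement for oxygen supplementation". Section 4.5 has no outcome for it, and section 6.4 does not name it among the variables to be modelled. Section 4.6 collects the following on oxygen:

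- at baseline, "Type of respiratory support at randomization (i.e., low-flow oxygen, HFNC, NPPV");
- the type of support at each PaO2/FiO2 reading (days 1, 3, 7 and 14);
- the WHO score at days 3, 7 and 14;
- HFNC as yes or no.

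No start or stop date is listed for HFNC or low-flow oxygen.

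**The concern.** Item h is an instruction to discard information. After NPPV, IMV and NPPV again, the end of the first NPPV session and the start of the second are not kept. The stored NPPV interval therefore runs across the intubated period and across any days without ventilation after extubation. Days of ventilation and days free of it are a secondary objective and the first secondary outcome, and the day-28 row needs NPPV and IMV days separately. An analysis plan can choose how to combine dates, but it cannot recover dates that sites were told not to enter.

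The oxygen point is a separate mismatch. An objective is stated, but neither the outcome list, the named analyses nor the data list carries it forward. A comparison of oxygen duration between arms could not be computed from what is listed.

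**Working it through.** The protocol gives no figure to reproduce here, so the check is a count of days on an assumed course. The lengths below are illustrative and are not trial data.

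**Assumed course.** NPPV on days 1–4, IMV on days 5–14, then g unventilated days, then 3 more days of NPPV. Day 28 is the horizon.

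**True counts, for every g shown**
- NPPV: 4 + 3 = 7
- IMV: 10
- Ventilated: 7 + 10 = 17
- Ventilation-free: 28 − 17 = 11

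**What items h and i store**
- NPPV from day 1 to day 14 + g + 3, a length of 17 + g days
- IMV from day 5 to day 14, a length of 10 days, wholly inside the NPPV interval

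**Three ways to use the stored dates**
- Union of dates: ventilated days = 17 + g; ventilation-free = 28 − (17 + g) = 11 − g
- NPPV interval minus IMV days: (17 + g) − 10 = 7 + g
- Adding the two durations: (17 + g) + 10 = 27 + g; ventilation-free = 1 − g

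| Gap g | NPPV as stored (true 7) | NPPV minus IMV (true 7) | Ventilated, union (true 17) | Free, union (true 11) | Ventilated, sum | Free, sum |
|---|---|---|---|---|---|---|
| 0 | 17 | 7 | 17 | 11 | 27 | 1 |
| 1 | 18 | 8 | 18 | 10 | 28 | 0 |
| 3 | 20 | 10 | 20 | 8 | 30 | −2 |
| 5 | 22 | 12 | 22 | 6 | 32 | −4 |

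Three things follow.

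1. With contiguous sessions (g = 0) nothing essential is lost. The union is exact, and NPPV days are recovered by subtracting IMV.
2. With a gap, the best available derivation is wrong by exactly g days, and no other listed date identifies g.
3. Summing the durations, or reading NPPV days straight from item h, is wrong even when g = 0.

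**Oxygen.** Suppose a patient is known to be on oxygen at day 7 and off it at day 14, with no restart between. The last oxygen day could be any of days 7 to 13, which is seven possible values. For a patient still on oxygen at day 14, no later dated oxygen item is listed. Discharge date does not fill the hole, because nothing ties the end of oxygen to discharge.

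**The case against.** **The outcome is a composite and IMV has its own dates.** This stands. A reader might infer that ventilation days are necessarily miscounted, for instance 27 days instead of 17 in the contiguous course above. That figure needs the two durations to be added, and the protocol nowhere says they will be. The union gives 17 ventilated and 11 free days, which is correct. The derivation may also be set out in an analysis plan that is not shown.

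**The day-28 row may capture the counts directly.** This is possible, and item h would then not be their source. But the protocol does not say so, and it gives no rule for when the counts and the dates disagree.

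**The forms are not shown.** Section 5.2 says "Electronic case report forms (eCRFs) will be developed to collect all clinical and laboratory related information". The criticism therefore applies to the data list in section 4.6, not to a form that nobody reading the protocol can inspect.

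**Direction of bias.** A reader might infer that the error favours methylprednisolone, because fewer intubations in that arm would mean fewer affected patients. The documents do not support this. The error needs a patient who is intubated, is extubated and then restarts NPPV. If methylprednisolone improves survival among intubated patients, more of them could reach that state in its arm, and the error could run the other way.

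**Oxygen.** It would be too strong to say that nothing on oxygen is collected. The requirement reads "The type of respiratory support (low-flow oxygen therapy, HFNC, NPPV, IMV, ECMO) under which the PaO 2 /FiO 2 is obtained must be always specified", and WHO scores are recorded as well. These are snapshots that bracket a stop date without giving a duration. The list of continuous variables in 6.4 is also open-ended, so an oxygen analysis is not excluded. It would still lack dates.

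**Conclusion.** The point holds in a limited form. The re-initiation rule in item h makes an unventilated gap before restarted NPPV unrecoverable. In each such patient, the union of dates overstates ventilated days and understates ventilation-free days by the length of the gap (20 against 17 ventilated days, and 8 against 11 free days, for a 3-day gap). The rule also invites double counting with IMV, and the protocol does not reconcile it with the day-28 counts.

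This rests on two assumptions: that item h means first start and last end, and that the day-28 counts are not collected independently of it. How often these courses and gaps occur is not given, so the effect on the arm means cannot be sized and its direction is undetermined.

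On oxygen, objective (d) cannot be measured as a duration from the listed data and has no matching outcome or named analysis. This part does not depend on the assumptions above.

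Only secondary endpoints are touched. The primary outcome, survival at 28 days, is unaffected. The changes should be made, but they do not put the main comparison in question.

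**What to change.** 1. In section 4.6, replace the re-initiation rule in item h with start and end dates for every NPPV episode, and do the same for IMV in item i.
2. State that days of mechanical ventilation are the calendar days in the union of all NPPV and IMV episodes up to day 28, and that the total, invasive and noninvasive counts in the day-28 row come from those same episode dates.
3. For objective (d), choose one of two routes. Either add stop dates for low-flow oxygen and HFNC (with start dates where support begins after randomization) and a matching outcome in 4.5 with its analysis in 6.4, or delete the objective.

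The cost is a few extra dates per patient, taken from the chart, and repeating date fields in the forms, which section 5.2 describes as still to be developed. Deleting objective (d) adds no data collection.

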##### 1. Arm 1 (methylprednisolone, MP):

- A. On day 1, loading dose of MP 80 mg IV in 30 minutes, promptly followed by continuous infusion of MP 80 mg/day in 240 mL of normal saline at 10 mL/h.
- B. From day 2 to day 8: infusion of MP 80 mg/day in 240 mL of normal saline at 10 mL/h.
- C. From day 9 and beyond:
  - a) If not intubated patient and  $\text{PaO}_2/\text{FiO}_2 > 200$ , taper to MP 20 mg IV in 30 minutes three times a day for 3 days, then MP 20 mg IV twice daily for 3 days, then MP 20 mg IV once daily for 2 days, then switch to MP 16 mg/day PO for 2 days, then MP 8mg/day PO for 2 days, then MP 4mg/day PO for 2 days;
  - b) If intubated patient or  $\text{PaO}_2/\text{FiO}_2 \leq 200$  with at least 5 cmH2O CPAP, continue infusion of MP 80 mg/day in 240 mL of normal saline at 10 mL/h until  $\text{PaO}_2/\text{FiO}_2 > 200$  then taper as in a)

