##### 2. Arm 2 (dexamethasone, DM)

- A. DM 6 mg IV in 30 minutes or PO from day 1 to day 10 or until hospital discharge (if sooner).
- B. After day 10 study treatment is interrupted.

Both methylprednisolone and dexamethasone are licensed in Italy. They have been widely used in clinical practice for many years and have proven efficacy in a variety of syndromes including COVID-19, with limited toxicity or adverse reactions.

Both drugs will be stored and administered in accordance with standard pharmacy procedures; they are both routinely available on the hospital formulary.

Both drugs will be given open label by either intravenous injection diluted to the treating dose in the appropriate diluent or *per os* according to treatment protocol.

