## 7. Safety measurements

### 7.1. Definitions

An adverse event is defined in the International Conference on Harmonization (ICH) Guideline for Good Clinical Practice as “any untoward medical occurrence in a patient or clinical investigation subject administered a pharmaceutical product and that does not necessarily have a causal relationship with this treatment.”

Events will be reviewed and classified by the site PI. The relationship of the event to the study drug and whether the event is an expected event or not will be assessed using the listing of adverse effects contained in the summary of product characteristics for the glucocorticoid drugs used.

The treating team has the primary responsibility for reviewing laboratory test results and determining whether an abnormal value in an individual study participant requires action. In general, abnormal laboratory without clinical significance (based on clinical judgment) should not be recorded as adverse events; however, laboratory value changes requiring therapy or adjustment in prior therapy are considered adverse. The investigators should liaise closely with the treating teams and remain aware of any such adverse events.

Serious adverse event (SAE) are defined as an adverse event that:

- Is fatal
- Is life threatening (places the participant at immediate risk of death)
- Requires in-patient hospitalization or prolongation of existing hospitalization
- Results in persistent or significant disability/incapacity
- Causes a congenital anomaly/birth defect
- Other significant medical hazard

However, since both the study drugs have been in wide clinical use for many years, their effects and possible adverse events are well recognized. As such, although adverse events may occur, we would not anticipate that they would be unexpected or widely divergent from established frequencies. Rarely, life threatening adverse reactions can occur with the use of any glucocorticoid. Other serious adverse events might include hyperglycemia, psychosis, depression or other psychic disorder, increased liver enzymes, venous thrombosis, wound healing impairment. However, multiple meta-analyses, involving thousands of critically ill patients with sepsis or ARDS, have demonstrated a relatively low-dose and short treatment courses like the ones proposed in this study are rarely associated with serious complications.(13)

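### Complications in item o are limited to the hospital stay and carry no onset date, so observation time can differ by arm and can end while methylprednisolone is still being given

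*Protocol*

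**What the plan says.** Section 4.6 has two safety items in its list of other data to be collected. Item n is "Adverse events related to study treatment (Anaphylaxis, Agitation, Psychosis, Insomnia, Hyperglycemia/diabetes of new onset, Other: specify". Item o begins "In-hospital complications (Bradycardia, Diarrhea, Increased liver enzymes, Hypotension, Hypokalemia" and goes on to superinfection, renal failure, arrhythmia, pulmonary embolism and others. Neither asks when the event began. Other entries in the same list do ask for dates, for example "Tracheostomy (yes/no; if yes specify date of tracheostomy"; so do the entries for NPPV, IMV, ECMO and protocol deviations.

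The list is attached to the day-28 row, which ends with "days of noninvasive mechanical ventilation) and final data collection". The hospital discharge row below it adds only "Patient's outcome determined (mortality, days of hospitalization".

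The regimens in section 4.3 differ in length and route. Arm 1 has eight days of infusion, then a stepped IV taper, "then switch to MP 16 mg/day PO for 2 days, then MP 8mg/day PO for 2 days, then MP 4mg/day PO for 2 days". Branch b of Arm 1 continues the infusion until an oxygenation threshold is met, with no limit in days, and Arm 1 has no clause on discharge. Arm 2 is IV or oral, "from day 1 to day 10 or until hospital discharge (if sooner".

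The last paragraph of section 7.1 promises that every death and adverse event will be captured and included in the final analysis. It sets no limit by place or by day.

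**The concern.** Section 3 makes safety, alongside efficacy, an aim of the trial, and section 7.3 sends safety outcomes to the DSMB at the interim analyses. A fair comparison of complications needs the same observation window in both arms. Item o's window closes at discharge. Discharge happens after randomization, and length of stay is itself compared by arm (section 4.5). The regimens also give different reasons to stay in hospital, because one requires IV drug for at least 16 days and the other can be taken orally from the start.

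Item o matters because it is the only listed set of complications that is not confined to events judged related to study drug. (One entry, shock, even excludes drug-induced cases.) Item n depends on attribution, which under section 7.1 is made by the site investigator, and under section 5.1 the trial is open label.

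A later analysis plan cannot repair this. Onset dates and post-discharge events that were never collected cannot be recovered.

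**Working it through.** The protocol states no total methylprednisolone duration, so there is no figure to reproduce. The timeline follows from the steps in section 4.3.

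**Inputs (Arm 1).** Infusion runs on days 1 to 8 at least; call its last day d. The IV taper steps last 3, 3 and 2 days. The oral taper steps last 2, 2 and 2 days.

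**Formulas.**
- IV taper = 3 + 3 + 2 = 8 days; oral taper = 2 + 2 + 2 = 6 days; whole taper = 14 days.
- Last IV day = d + 8.
- Last day of study drug = d + 14.

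| Infusion through day d | Last IV day | Last day of study drug | Days beyond day 28 |
|---|---|---|---|
| 8 (shortest course) | 16 | 22 | 0 |
| 14 | 22 | 28 | 0 |
| 15 | 23 | 29 | 1 |
| 20 | 28 | 34 | 6 |
| 28 | 36 | 42 | 14 |

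Treatment passes day 28 when d + 14 > 28, that is, when d is 15 or more. In Arm 2 the last day is day 10 at the latest, and never after discharge.

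**Setting these dates against item o.**

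1. *Discharge during the taper.* On the shortest course the oral steps are days 17 to 22. A patient who goes home in that period leaves item o's window with up to 6 days of study drug still to take. The same cannot happen in Arm 2, where treatment stops at discharge.
2. *Unequal windows.* Suppose, for illustration, a constant daily complication rate h that is equal in both arms. The expected count per patient is h × w, where w is the mean number of days in item o's window. With no true difference, the ratio of counts is then w(Arm 1) / w(Arm 2). It equals 1 only if the windows are equal. The protocol gives neither value of w, so the ratio cannot be computed.
3. *Opposing effects.* A longer stay in Arm 1 would add events to its count. Leaving out the oral taper after discharge would remove events from it. The net direction cannot be derived.
4. *Before randomization.* A hospital stay begins at admission. Section 4.6 records the dates of hospitalization and randomization as separate baseline items. Without an onset date, a complication between the two cannot be told from one after randomization.
5. *After day 28.* For d of 15 or more, study drug continues past the day-28 row. The discharge row does not mention complications, and the list does not say whether items n and o stay open.

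**The case against.** The strongest reply is that safety data are not confined to item o. Item n has no hospital limit, and section 7.1 promises that all adverse events are recorded. Section 7.2 runs its reporting clock from first knowledge, with no day-28 cut-off. A reader might infer that events after discharge are excluded from the trial's safety data altogether, and the protocol does not support that. The reply does not remove the point, though. Item n needs a judgement of relatedness, and section 7.2 defines its events as unexpected, possibly related and a source of increased risk. The promise in section 7.1 does not agree with a complication list confined to the hospital stay.

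A reader might also infer that collection closes at day 28. That is not stated. The same list holds the dates of de-escalation completion, discharge and death, all of which can fall later. A patient in branch b is intubated or on CPAP when the infusion is extended, so may well still be in hospital and within item o. What stands is that the list does not say clearly how far it runs.

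A third inference is that the comparison is already biased against methylprednisolone. That would need discharge days by arm, which the protocol does not give, and section 2.2 names a shorter hospital stay as a benefit sought from methylprednisolone.

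Finally, the remark in section 7.1 that "relatively low-dose and short treatment courses like the ones proposed in this study are rarely associated with serious complications" might seem to conflict with a course of at least 22 days. It rests on a cited source that is not at hand, and the protocol does not define short, so it carries no weight here.

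It is fair to say that eCRF detail comes later (section 5.2), and that HFNC, pronation and remdesivir also have no dates. Those are not safety events whose timing relative to randomization and treatment matters for a comparison by arm.

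**Conclusion.** The point holds as a risk of unequal observation and as an inconsistency between sections. Item o is tied to the hospital stay, and neither n nor o is dated. The regimens differ enough in route and length (last dose on day 22 or later, against day 10 at the latest) for the window to differ by arm. It can end while methylprednisolone continues: at discharge in the oral taper, and possibly at day 28 when the infusion runs through day 15 or later. The day counts assume that the Arm 1 steps are followed as written, without gaps. The size and net direction of any bias are unknown. The primary outcome is not affected. The change is a cheap improvement that has to be made before data are collected.

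**What to change.** - Define item o as complications from randomization to day 28, in or out of hospital.
- Add an onset date to every event in items n and o.
- Ask about post-discharge events when day-28 status is determined.
- Base the comparison of complications by arm on that fixed window.
- For patients still on study drug after day 28, record later events and report them separately.
- Reconcile section 4.3 (Arm 1 duration), section 4.6 (the day-28 list and the discharge row) and section 7.1 (all adverse events recorded) so that they state one observation window. This concerns what is observed and for how long; no treatment rule needs to change on this account.

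The cost is a few eCRF fields, some questions at a point where survival status is needed anyway, and one further entry for patients treated beyond day 28. If a site would otherwise take day-28 status from records alone, it also needs a call to the patient. The small downside is that post-discharge events will be partly patient-reported; the onset dates and a marker for place of occurrence would let these be shown apart.
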